## 7. DISCONTINUATION OF STUDY INTERVENTION AND PARTICIPANT DISCONTINUATION/WITHDRAWAL

### 7.1. Discontinuation of Study Intervention

A participant's study intervention must be discontinued if:

- The participant withdraws consent to receive study intervention.
- The investigator believes that for safety reasons or tolerability reasons (eg, AE) it is in the best interest of the participant to discontinue study intervention.

- The participant has a QTcF prolongation (defined as a QTcF value  $\geq 500$  ms, or an increase from baseline of  $>60$  ms) at any given time point (confirmed by repeat ECGs).
- The participant requires treatment with any of the prohibited medications listed in Section 6.8, [Concomitant Therapy](#).
- The participant becomes pregnant. Refer to Section 10.5, [Appendix 5: Contraceptive Guidance](#).
- Noncompliance with study intervention administration as defined in [Table 3](#).
- The participants discontinued administration of study intervention before Week 48 in Group A, Week 60 in Group B or OPW48 in optional cohort.

If a participant discontinues study intervention before Week 48 in Group A, Week 60 in Group B or OPW48 in the optional cohort, the participant will receive the assessments of early discontinuation or withdrawal.

The early discontinuation visit assessment will be performed within 7 days of the investigator's discretion to discontinue treatment with study intervention, unless the participant withdraws consent. Study intervention assigned to the participant who discontinued study intervention may not be assigned to another participant.

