#### **7.1.2. QTc Stopping Criteria**

Refer to Section 8.2.3, [Electrocardiograms](#).

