#### **7.1.3. Temporary Discontinuation**

Participants will be temporarily discontinued from study treatment at the investigator's discretion. Few situations are specified in Section 8.2.3, [Electrocardiograms](#) and Section 8.2.6 [Management of Common Expected Toxicities](#).

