#### **7.1.4. Rechallenge**

Instructions on BDQ interruption and resumption are specified in [Table 3](#).

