### **8.2.3. Electrocardiograms**

During the collection of ECGs, participants should be in a quiet setting without distractions (eg, television, cell phones). Participants should rest in a supine or sedentary position for at least 5 minutes before ECG collection and should refrain from talking or moving arms or legs. If blood sampling or vital sign measurement is scheduled for the same time point as ECG recording, the procedures should be performed in the following order: vital signs, ECG(s), blood draw.

At each time point at which triplicate ECGs are required, 3 individual ECG tracings should be obtained as closely as possible in succession, but no more than 2 minutes apart. The full set of triplicates should be completed within 5 minutes and must be of good quality (stable baseline, free of interference and artefact). ECGs will be recorded at a paper speed of 25 mm per second until 4 regular consecutive complexes are available. If the record is unclear due to the noise, ECGs will be repeated after 1 or 2 minutes, and the clearer recording will be adopted as an original recording. In principle, 2 original ECG recordings will be provided. One original recording will be stored at the study site and another will be sent to a central cardiologist designated by the sponsor for review. Submission of ECG to a central cardiologist will be done by transmission or send a hardcopy ECG if transmission is not possible for any reasons (refer ECG manual for details). The ECG machine dedicated for this study must be used. All tracings will be transmitted for blinded central analysis. Participants found to have a QTcF  $\geq 500$  ms or an increase from baseline (mean of triplicates on Day 1) of  $>60$  ms on ECG at any point during the treatment period will be further investigated. The ECG should be repeated and if confirmed, the investigator should attempt to identify the cause, including checking and correcting abnormal  $K^+$ ,  $Ca^{+2}$ , and  $Mg^{+2}$ . If the participant is taking any drugs suspected of causing QT prolongation, they should be withheld, and the tests repeated after sufficiently long washout to try to identify the cause. Any QTcF prolongation to  $\geq 500$  ms or an increase from baseline (mean of triplicates on Day 1) of  $>60$  ms while on study intervention is considered a notable event and should be reported immediately to the sponsor.

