### **QTcF Prolongation**

If a single ECG shows QTcF  $\geq 500$  ms or an increase from baseline (mean of triplicates on Day 1) of  $>60$  ms, then complete additional triplicate ECGs, evaluate the mean QTcF, and record results on an unscheduled visit form.

If triplicate ECGs confirm a mean QTcF  $\geq 500$  ms or an increase from baseline of  $>60$  ms, the following will be done:

- the investigator must assess potential causes of the abnormality including at a minimum a check and correction of electrolyte imbalances ( $K^+$ ,  $Mg^{+2}$ ,  $Ca^{+2}$ ), review and adjust combination medications as necessary (eg, temporarily discontinuation of BDQ and CAM), and obtain weekly duplicate/triplicate ECGs until resolution,
- if after 2 weeks mean QTcF is  $\geq 500$  ms or increase from baseline of  $>60$  ms, the investigator must permanently stop the study intervention, and continue weekly triplicate ECGs until resolution.

Weekly triplicate ECG monitoring for participants who have recovered from QTcF  $\geq 500$  ms or increase from baseline of  $>60$  ms may be discontinued if over 3 consecutive weeks the triplicate ECGs demonstrate a mean QTcF  $<500$  ms or one time increase of  $\leq 60$  ms. Participants who meet these criteria can be switched to less frequent ECG monitoring per Section 1.3, [Schedule of Activities \(SoA\)](#). If mean QTcF  $<500$  ms or increase of  $\leq 60$  ms is not demonstrated, then weekly triplicate ECGs will be continued at least until the end of the last dose of BDQ plus 4 weeks due to the long half-life of BDQ. At that point, if mean QTcF  $<500$  ms or increase of  $\leq 60$  ms is demonstrated, weekly triplicate ECGs can be switched to less frequent ECG monitoring per Section 1.3, [Schedule of Activities \(SoA\)](#). Otherwise if mean QTcF  $<500$  ms or increase of  $\leq 60$  ms is not demonstrated, the investigator judges whether weekly triplicate ECGs will be continued or be switched to less frequent ECG monitoring per Section 1.3, [Schedule of Activities \(SoA\)](#).

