#### **Cardiac Rhythm Disturbances**

The following text describes the minimum requirements for the management of cardiac rhythm disturbances; however, additional management decisions are at the investigator's discretion.

Grade 1 (asymptomatic) or Grade 2 (asymptomatic, transient rhythm abnormality not requiring any treatment) cardiac rhythm disturbances:

Participants may continue to take the study intervention and should be carefully evaluated and followed closely.

Grade 3 (recurrent, persistent, symptomatic arrhythmia requiring treatment) or Grade 4 (unstable dysrhythmia requiring hospitalization and treatment) cardiac rhythm disturbances:

Participants will permanently discontinue the study intervention. QTcF prolongation that results in discontinuation of the study intervention will be reported as AE term of "QT prolonged" of

Grade 2 if no symptoms are present. If symptomatic, then a higher grade may be reported as per the definitions above.

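### Protocol 7.1 stops treatment at any confirmed QTcF prolongation while 8.2.3 stops it only if prolongation persists after 2 weeks, and 6.7 labels some loading doses directed by Table 3 as overdoses

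*Protocol*

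**What the plan says.** **QTcF.** Protocol 7.1 lists the conditions under which study intervention must be discontinued. One is a QTcF of 500 ms or more, or a rise from baseline above 60 ms, "at any given time point (confirmed by repeat ECGs". The bullet has no waiting period and no exception.

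Other places treat the same finding differently:

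- Protocol 7.1.2, on QTc stopping, says only "Refer to Section 8.2.3". Protocol 7.1.3, on temporary discontinuation, says "Few situations are specified in Section 8.2.3". Protocol 7.1.4 says "Instructions on BDQ interruption and resumption are specified in" Table 3.
- Protocol 8.2.3 says of drugs suspected of prolonging QT that "they should be withheld, and the tests repeated after sufficiently long washout to try to identify the cause". Once triplicate ECGs confirm the finding, the investigator is to look for causes and "review and adjust combination medications as necessary (eg, temporarily discontinuation of BDQ and CAM". If either limit is still exceeded after 2 weeks, "the investigator must permanently stop the study intervention, and continue weekly triplicate ECGs until resolution".
- Protocol 8.2.6, under cardiac rhythm disturbances, says "QTcF prolongation that results in discontinuation of the study intervention will be reported as AE term of" a stated QT term. This presupposes that some prolongation does not lead to discontinuation.

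SAP 5.3.2 treats a participant with treatment discontinuation before Week 24 as a nonconverter. It does not define treatment discontinuation.

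**Overdose.** Protocol 6.7 sets one bedaquiline limit, 400 mg in 24 hours, up to 14 days after the first dose. From 15 days it sets another, 200 mg in 72 hours, with a 24-hour tolerance. Table 3 (Protocol 6.4) tells sites what to do when loading is interrupted. After 14 days or less they complete the remaining loading doses. After more than 14 days they restart loading, and after more than 30 days they may not restart. Protocol 6.7 makes no exception for these doses.

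**The concern.** Both points concern instructions that a site must follow, and in each case obeying one section breaches another.

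On QTcF, the two sections differ only for prolongation that resolves within 2 weeks. A site that holds, corrects the cause and restarts follows 8.2.3 and Table 3 but breaches the 7.1 bullet. A site that stops at first confirmation follows the bullet but gives up a restart that 8.2.3 permits. The same ECG can then yield a forced nonconverter at one site and a possible converter at another, in an open-label trial whose primary endpoint counts discontinuation as failure. Protocol 2.3.1 attributes QT risk to bedaquiline and clarithromycin. Only Group A receives bedaquiline before Week 24, so literal use of 7.1 would be expected to fall more on Group A, against the new regimen.

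On overdose, dosing that Table 3 directs meets the overdose definition. Protocol 6.7 then calls for immediate contact with the medical monitor, a decision on interruption or dose reduction, and an eCRF entry. Protocol 10.4.4 lists overdose as a special reporting situation. The safety data would contain overdoses that are only artefacts of the definition.

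**Working it through.** The plan gives no figure for either point. The check compares the texts and counts days.

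**1. QTcF rules side by side**

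| Course after confirmation | Protocol 7.1 bullet | Protocol 8.2.3 |
|---|---|---|
| Still prolonged after 2 weeks | Stop | Permanent stop |
| Resolved within 2 weeks | Stop | No stop required; restart possible under Table 3 |

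The rules disagree only in the second row.

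How much treatment does such a hold cost?

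- Planned bedaquiline dosing days to Week 24 (Table 2: daily in Weeks 1-2, then twice weekly): 14 + 22 × 2 = 58.
- A 14-day hold in the maintenance phase misses at most 2 × 2 = 4 of these.
- Compliance by the SAP Appendix 7 formula: 54/58 = 93.1%, above the 80% limit for a complier.

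Such a participant is a complier by the SAP's own rule, yet the 7.1 bullet read literally would make the same participant a nonconverter. With 62 per arm (Protocol 9.2), each would-be converter reclassified moves that arm's rate by 1/62 = 1.6 points.

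**2. Loading doses against the 6.7 limits**

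Loading is 14 daily doses of 400 mg. Let m doses be taken on Days 1 to m, followed by k days off. The remaining 14 − m doses then fall on Days m + k + 1 to 14 + k.

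Past the cut-off, a single 400 mg dose exceeds 200 mg whether the window is 72 or 48 hours. Daily dosing gives 3 × 400 = 1,200 mg per 72 hours. The number of resumed doses that count as overdoses is therefore:

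- min(14 − m, k) if 15 days means Day 15;
- min(14 − m, k − 1) if it means 15 days after the first dose, which is Day 16.

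| m | k | Days of resumed doses | Overdoses, Day 15 reading | Overdoses, Day 16 reading |
|---|---|---|---|---|
| 7 | 3 | 11-17 | 3 of 7 | 2 of 7 |
| 7 | 5 | 13-19 | 5 of 7 | 4 of 7 |
| 7 | 7 | 15-21 | 7 of 7 | 6 of 7 |
| 4 | 10 | 15-24 | 10 of 10 | 9 of 10 |
| 7 | 14 | 22-28 | 7 of 7 | 7 of 7 |

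For m from 1 to 13 and k from 2 to 14, both formulas give at least 1. Every such interruption therefore produces at least one labelled overdose on either reading. One-day gaps are left out, because the missed-dose column of Table 3 may cover them.

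For restarted loading, k is at least 15 and m at least 1, so the first restarted dose falls on Day 17 or later. If the first dose in 6.7 means the original one, 14 of 14 restarted doses count as overdoses. If it means the restarted one, 0 of 14 do.

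**The case against.** The strongest reply on QTcF is that the protocol reconciles itself. The 7.1 bullet does not say permanently. Subsections 7.1.2 to 7.1.4 send the reader to 8.2.3 and Table 3, and 8.2.6 assumes that not every prolongation ends treatment. The specific algorithm then governs the general bullet. SAP 5.6.2 tabulates interruption apart from discontinuation, so a hold is not naturally a discontinuation. This stands as the likely intention. It does not remove the conflict. The bullet is mandatory and unconditional, 7.1 attaches early-discontinuation assessments to stopping, and the SAP distinction is not carried into 5.3.2.

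SAP version 4 also records every subject as a complier at 80% or more, which suggests limited practical reach. That is fair, but at 93.1% a 14-day maintenance hold passes the same test, so the statement does not rule such holds out.

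Several stronger readings are tempting and are not supported:

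- That 8.2.3 prescribes a 2-week hold. The hold is an example; the 2 weeks is when persistence is judged.
- That a resolved QTcF episode bars entry to the optional cohort. Protocol 6.8.2 tests its criteria when the decision to switch is made, so a resolved episode does not naturally count.
- That every loading dose taken after an interruption is an overdose. Only those past the cut-off are.
- That the late maintenance dose rule in Table 3 breaks the 72-hour minimum. Table 2 sets that minimum, and the schedule to be resumed naturally includes it.
- That the alternative limits for reducing weekly ECGs release participants who are still prolonged. The rule covers only those who have recovered, and it governs ECG frequency, not dosing.

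**Conclusion.** Protocol 7.1 and 6.7 are wrong as written on two specific points.

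The 7.1 QTcF bullet conflicts with 8.2.3 for prolongation that resolves within 2 weeks. The conflict reaches the primary endpoint only if a site applies 7.1 literally, or if a hold is classed as treatment discontinuation under SAP 5.3.2. Its size is 1.6 points in one arm per would-be converter reclassified. The documents give no rate of resolving prolongation, so neither a number affected nor a loss of power can be stated, although a reader might infer one.

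The 6.7 limits label Table 3 loading doses as overdoses after any loading interruption of 2 to 14 days. The count is min(14 − m, k) or min(14 − m, k − 1), depending on how the 15-day cut-off is read. For restarted loading it is 14 or 0 of 14, depending on which first dose is meant. These counts assume one 400 mg dose a day with no further gaps. How often loading is interrupted is not known from the documents.

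**What to change.** 1. Reword the 7.1 bullet as QTcF prolongation meeting the permanent stopping rule in Section 8.2.3.
2. State in SAP 5.3.2 that a temporary hold permitted by the protocol is not treatment discontinuation.
3. Define the 6.7 overdose limits by dosing phase: the 400 mg limit while loading doses are being given, including resumed or restarted ones, and the 200 mg limit in the maintenance phase.

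Two clarifications are optional: repeat the 72-hour minimum beside the late-dose rule in Table 3, and tidy the ECG-reduction wording in 8.2.3 so that both limits must be met.

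The cost is a few words in 7.1 and 6.7 by clarification or amendment, a site letter, and one SAP sentence. Design, sample size and data collection do not change.

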#### **7.1.1. Liver Chemistry Stopping Criteria**

Refer to Section 8.2.6 [Management of Common Expected Toxicities](#).

#### **7.1.2. QTc Stopping Criteria**

Refer to Section 8.2.3, [Electrocardiograms](#).

#### **7.1.3. Temporary Discontinuation**

Participants will be temporarily discontinued from study treatment at the investigator's discretion. Few situations are specified in Section 8.2.3, [Electrocardiograms](#) and Section 8.2.6 [Management of Common Expected Toxicities](#).

#### **7.1.4. Rechallenge**

Instructions on BDQ interruption and resumption are specified in [Table 3](#).

### **7.2. Participant Discontinuation/Withdrawal From the Study**

A participant will NOT be automatically withdrawn from the study if he or she has to discontinue study intervention before Week 48 (Group A), Week 60 (Group B), or OPW48 (the optional cohort). A participant will be withdrawn from the study for any of the following reasons:

- Lost to follow-up
- Withdrawal of consent
- Death

When a participant withdraws before study completion, the reason for withdrawal is to be documented in the eCRF and in the source document.

Participants will be encouraged to complete the early discontinuation visit assessments, which is to be scheduled within 7 days of investigator's discretion to discontinue treatment with study intervention. If the reason for withdrawal from the study is withdrawal of consent, then no additional assessments are allowed.

### **Withdrawal of Consent**

A participant declining to return for scheduled visits does not necessarily constitute withdrawal of consent. Alternate follow-up mechanisms that the participant agreed to when signing the consent form apply (eg, consult with family members, contacting the participant's other physicians, medical records, database searches, use of locator agencies at study completion,) as local regulations permit.

#### **7.2.1. Withdrawal From the Use of Research Samples**

Collection of optional samples for research is not planned in the study.

### **7.3. Lost to Follow-up**

To reduce the chances of a participant being deemed lost to follow-up, prior to randomization attempts should be made to obtain contact information from each participant, eg, home, work, and mobile telephone numbers, and email addresses for both the participant as well as appropriate family members.

A participant will be considered lost to follow-up if he or she repeatedly fails to return for scheduled visits and is unable to be contacted by the study site. A participant cannot be deemed lost to follow-up until all reasonable efforts made by the study-site personnel to contact the participant are deemed futile. The following actions must be taken if a participant fails to return to the study site for a required study visit:

- The study-site personnel must attempt to contact the participant to reschedule the missed visit as soon as possible, to counsel the participant on the importance of maintaining the assigned visit schedule, to ascertain whether the participant wishes to or should continue in the study.
- Before a participant is deemed lost to follow up, the investigator or designee must make every reasonable effort to regain contact with the participant (where possible, telephone calls, e-mails, fax, and, if necessary, a certified letter to the participant's last known mailing address, or local equivalent methods). These contact attempts should be documented in the participant's medical records.
- Should the participant continue to be unreachable, they will be considered to have withdrawn from the study.
- Should a study site close, eg, for operational, financial, or other reasons, and the investigator cannot reach the participant to inform them, their contact information will be transferred to another study site.

## 8. STUDY ASSESSMENTS AND PROCEDURES

### Overview

The Schedule of Activities (SoA) summarizes the frequency and timing of efficacy, PK, and safety measurements applicable to this study.

The following time windows are allowed:

- For visit Weeks 2, 4, 6, 8, 10, and 12 ( $\pm 2$  days)
- For visit Weeks 16, 20, and 24 ( $\pm 3$  days)
- For visit Weeks 28, 32, 36, 40, 44, 48, 52, 56, and 60 ( $\pm 4$  days)

In case of scheduling visit according to above time windows, the investigators should ensure that 4-week sputum collection interval does not fall below 25 days.

All PRO (SGRQ and QOL-B NTM module) assessments should be conducted/completed before any tests, procedures, or other consultations to prevent influencing participant perceptions. The questionnaires will be completed by the investigator after interviewing the participant and the data will be entered into the eCRF by the investigator/study-site personnel. Refer to the PRO completion guidelines for instructions on the administration of PROs.

If multiple assessments are scheduled for the same timepoint, it is recommended that procedures be performed in the following sequence: noninvasive procedures should be collected first before invasive procedure (questionnaire/interview/ECG, vital sign/physical examination/CT scan/audiology/visual examinations/fundoscopy, then sputum sample collection, and blood sampling). ECG and blood collections for PK assessments should be kept as close to the specified time as possible. Other measurements may be done earlier than specified timepoints if needed. Actual dates and times of assessments will be recorded in the source documentation and eCRF.

The total blood volume for the study is approximately 68 to 115.5 mL (52 mL [Group A] for pharmacokinetics and 20 mL [Group B], and 2 mL for pregnancy testing [women of childbearing potential only]).

The total blood volume to be collected from each participant will be approximately 68 to 115.5 mL.

For each participant, the maximum amount of blood drawn from each participant in this study will not exceed 115.5 mL.

Repeat or unscheduled samples may be taken for safety reasons or for technical issues with the samples.

If the unscheduled PK samples are taken, the date and the time of the blood draw must be recorded.

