### 8.1.2. Clinical Assessments in MAC-LD

#### *SGRQ*

CCI

[REDACTED]

Paper-based SGRQ will be provided by the sponsor. It will be recommended that the paper questionnaire be received from the investigator or study staff at the site visit indicated in Section 1.3, [Schedule of Activities \(SoA\)](#) and that subject perform a self-assessment in a waiting room, etc. in an environment where the subject can be instructed on the contents including the assessment period of the questionnaire. It will be allowed that the investigator may also complete the assessment by interviewing (read out each question as written) and obtain the answers from the subject, if the investigator judges that the subject's understanding of the questionnaire including the assessment period is insufficient, etc.

The SGRQ author instructs in the SGRQ manual that “Do not allow patients to take the SGRQ home to be completed since the sponsor cannot be sure that it will be completed without the help of family or friends”.

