## IMPORTANT MATTERS RELATED TO COVID-19 AND COORDINATION OF STUDY CONDUCT

- During the course of COVID-19 pandemic, it may not be possible to visit the study site or perform tests as specified in the protocol. Temporary measures may therefore be taken if, in the judgment of the sponsor and the investigator (co-investigator), it is appropriate to continue the subject's study treatment and to maintain the integrity of the study. Specific measures may be required and should be implemented in accordance with applicable local laws, regulations, guidelines and procedures, including:. These deviations will be handled as "COVID-19 -related".
  - If a subject is unable to visit within the acceptable visit window, the subject may visit outside of the visit window.
  - If it becomes necessary to reduce the time spent for tests or if some tests are limited, etc. at the time of visit to the study site, the following actions are acceptable;
    - Sputum collection at the study site: If sputum collection at home is not possible, 2 collections are required at the study site. In such case, if good sputum specimen can be collected at the first time at the study site, no second collection will be acceptable
    - Sputum collection at home: If sputum collection including induced sputum specimen is not possible or limited at the study site, the submission of at least 1 spontaneous sputum specimen collected at home is acceptable without second collection at the study site. And, both sputum specimens at home and at the study site are not obtained and re-collection at home or at the study site is not possible, the submission of sputum specimens at this time point may be omitted
    - If two blood samplings for PK will be drawn at the study site, 2nd blood sampling may be drawn between 30 minutes to 4 hours after the intake. When the timing of 2nd blood sampling is changed, the timing of ECG measurement should be adjusted according to the protocol
    - Assessments of the SGRQ and QOL-B NTM module may be self-administered at home prior to the visit, provided the subject has an environment in place to receive the explanations to his/her queries to these questionnaires. If both assessments are performed after site visit, if only one assessment is feasible, the SGRQ assessment will take precedence and any missing QOL-B NTM module assessment will be allowed

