**VERSION HISTORY****Table 1: SAP Version History Summary**

SAP Version	Approval Date	Change	Rationale
1	26 February 2021	Not Applicable	Initial release
2	25 April 2022	
 
Appendix 11 (Unblinding Plan), Appendix 12 (Agreement on the Unblinded Information Handling) and Appendix 13 (Running Log of Default Unblinders) were added.
 
The definition of culture reversion (relapse or reinfection) was added in Section 5.5.2.
 
Other changes were made to keep consistency with the protocol.
 
	
 
Detailed unblinding plan which was added in the protocol Amendment 6.
 
Clarified the definition of culture reversion.
 

3	24 May 2024	
 
Appendix 11 (Unblinding Plan) and Appendix 12 (Agreement on the Unblinded Information Handling) were updated.
 
Region and duration of previous therapy for MAC-LD were added in Appendix 3 (Demographics and Baseline Characteristics).
 
Other changes were made to keep consistency with the protocol and correct errors.
 
	
 
Clarified unblinders and scope of blinding.
 
Reflected study design changes from protocol Amendment 7 to Amendment 8.
 

4	31 January 2025	
 
Definition of analysis phase was modified to include data after switching to individualized treatment regimen in the investigational phase.
 
Visit window for optional cohort was modified to use the start date of optional treatment as baseline.
 
Region (Japan, non-Japan) was added as a stratification factor in statistical tests.
 
The supplementary estimand considering for treatment non-compliers was deleted.
 
Other changes were made for clarification, error correction or consistency with other study documents.
 
	
 
Investigational treatments are included in individualized treatment regimen.
 
Variable washout period before start of optional treatment is considered.
 
Based on the advice from PMDA.
 
All subjects are compliers defined as 80% or more compliance.
 

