**5.4.2.2.6. St. George's Respiratory Questionnaire (SGRQ)**

The changes from baseline in total score of SGRQ and domain scores will be summarized descriptively at Weeks 24, 48, and 60. For the total score of SGRQ at Week 24, the difference in the change from baseline between the treatment groups will be provided using an analysis of covariance (ANCOVA) model. The baseline total score will be used as covariate in the analysis.

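### Protocol Section 8 has the investigator complete the SGRQ and QOL-B NTM module by interview, which contradicts the self-completion rule in 8.1.2 and adds avoidable interviewer bias to a supportive endpoint in an open-label trial

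*Protocol*

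**What the plan says.** Four places in the protocol bear on who fills in the questionnaires.

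- **Section 8, Overview**, on both instruments and without any condition: "The questionnaires will be completed by the investigator after interviewing the participant". The site then enters the data in the eCRF.
- **Section 8.1.2, SGRQ**, recommends that the "subject perform a self-assessment in a waiting room, etc. in an environment where the subject can be instructed". Interview is allowed, with the questions read aloud verbatim, "if the investigator judges that the subject's understanding of the questionnaire including the assessment period is insufficient" (an open-ended 'etc.' follows). The QOL-B and NTM module text carries the same default and the same exception. The SGRQ text also cites the instrument's manual: "Do not allow patients to take the SGRQ home to be completed since the sponsor cannot be sure".
- **Section 10.3.9** requires that whoever completed the baseline questionnaire also completes the later ones. It does not say whether that is the participant or a staff member.
- **COVID-19 Appendix**: "Assessments of the SGRQ and QOL-B NTM module may be self-administered at home prior to the visit", provided the participant can have queries answered.

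SGRQ total score change at Week 24 is a secondary endpoint (Protocol Section 3). SAP 5.4.2 classes it as supportive, and SAP 5.4.1 defines no key confirmatory secondary endpoints. SAP 5.4.2.2.6 gives the between-group difference from an ANCOVA: "The baseline total score will be used as covariate in the analysis". The SAP plans no summary or analysis by mode of completion.

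**The concern.** Section 8 and Section 8.1.2 give opposite defaults for the same two questionnaires, and a site can cite either. Under Section 8, every answer passes through an investigator who knows the assigned treatment. An interviewer's expectations can then colour how answers are drawn out or written down, and the effect may differ between arms.

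At stake is the SGRQ comparison at Week 24, the only patient-reported outcome with a planned between-group model (the QOL-B NTM module is summarised descriptively). If the mode of completion is not recorded, nobody can later check whether it was balanced between the arms. The bias is avoidable because 8.1.2 already describes the remedy.

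**Working it through.** **Text comparison.**

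| Question | Section 8 | Section 8.1.2 | Section 10.3.9 | COVID-19 Appendix |
|---|---|---|---|---|
| Who completes? | Investigator | Participant by default | Same person as at baseline, not named | Participant |
| Role of interview | Always | Exception | Not addressed | Not addressed |
| Where? | Not stated | At the site; manual advises against home | Not addressed | Home permitted |

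The amendment history suggests how this arose. Amendment 2 added the self-assessment method and lists 8.1.2 as the section changed. The Section 8 sentence looks like text that was not updated, but it remains operative.

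No other section settles the matter. Inclusion criterion 7 requires that no cognitive dysfunction affect completion of the questionnaires, so most participants should be able to complete them unaided. Section 10.3.10 lists patient-reported outcomes as source data entered directly in the eCRF, although 8.1.2 specifies paper forms. The mode actually used may therefore be hard to trace.

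**What the recorder knows.** Treatment is open-label (Protocol 4.2). Culture results are withheld from investigators and participants until the other Week 24 assessments are done, unless opened for clinical worsening (4.1 and 6.3). A Week 24 interviewer therefore normally knows the arm but not the conversion status. At Weeks 48 and 60 that protection no longer applies.

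**Size.** The documents give no SGRQ standard deviation, target difference or estimate of interviewer effect, so there is no plan figure to reproduce. The following is illustration only.

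- From the documents: 62 per group (Protocol 9.2), taken here as complete data.
- Assumed: SD of the baseline-adjusted change 10, 15 or 20 points; differential shift d between arm means of 1, 2 or 4 points; no true effect; a two-sided 5% comparison. SAP 5.4.2.2.6 states no level for this comparison.
- Formulas: SE = SD × √(2/62); false-positive rate = Φ(d/SE − 1.96) + Φ(−d/SE − 1.96).

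| SD | SE | d = 1 | d = 2 | d = 4 |
|---|---|---|---|---|
| 10 | 1.80 | 8.6% | 20.0% | 60.5% |
| 15 | 2.69 | 6.6% | 11.5% | 31.8% |
| 20 | 3.59 | 5.9% | 8.6% | 20.0% |

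Here d is the shift in an arm's mean relative to the other arm. If a fraction f of one arm is interviewed and each interviewed participant shifts by b points, d = f × b. With f = 25% and b = 4 (both assumed), d = 0.25 × 4 = 1 point, which at SD 15 gives 6.6% rather than 31.8%. Equal shifts in both arms cancel.

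**Region.** Protocol 6.3 stratifies randomisation by country. The SAP's main CMH tests, the generalized linear model and the log-rank test use region (Japan, non-Japan). The SGRQ ANCOVA adjusts for baseline score only. The CMH sensitivity analysis by MAC type (SAP 5.3.2.2) also leaves region out.

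**The case against.** The plan has real safeguards. Section 8 places the questionnaires before other procedures. Section 10.3.9 works against changing completer between baseline and Week 24. Where 8.1.2 allows an interview, it is scripted. No rule makes mode depend on arm. Sites also receive PRO completion guidelines, not available here, which may settle daily practice. All of this stands and limits the likely harm, but a supporting guideline does not remove a contradiction between two sections of the protocol.

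Several stronger readings are tempting, and the documents do not support them.

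- *The interviewer knows who converted.* Normally not at Week 24, because culture results are still withheld.
- *Self-completion would make the endpoint unbiased.* It would not. Participants know their treatment, so their own reporting bias stays.
- *Evidence that conversion helps patients is compromised.* The Week 24 ANCOVA compares randomised arms. SGRQ in converters is a separate, exploratory and descriptive analysis.
- *Home completion is uncontrolled.* The COVID-19 Appendix makes it a temporary, conditional measure and has affected data flagged as COVID-19-related. What remains is its conflict with the manual text in 8.1.2.
- *Leaving region out of the ANCOVA is an error.* SAP version 4 states that "Region (Japan, non-Japan) was added as a stratification factor in statistical tests", but the Amendment 8 summary names the CMH, generalized linear and log-rank analyses, and Protocol 9.4.4 gives the ANCOVA without region.
- *An ANCOVA in self-completers would settle the matter.* Under 8.1.2, those interviewed are mainly those judged to understand poorly. Mode is a post-randomisation feature, and restricting on it weakens the randomised comparison.

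**Conclusion.** The contradiction is plain in the current text, and the Section 8 sentence should change. Followed as written, it gives a person who knows the arm control over recording a patient-reported secondary endpoint, when the protocol already describes a better method. The same conflict affects the exploratory QOL-B NTM module.

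The size of any bias cannot be derived from the documents. At an assumed SD of 15 with 62 per group, a differential shift of 1 to 4 points in arm means would put the false-positive rate between 6.6% and 31.8%. The upper end requires nearly a whole arm to be interviewed and shifted the same way, which nothing in the documents shows. The consequence is confined to supportive and exploratory outcomes; the primary culture-conversion analysis is unaffected. Adding region to the ANCOVA is a worthwhile refinement, independent of the interviewer issue.

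**What to change.** 1. Replace the Section 8 sentence with the 8.1.2 rule: self-completion at the site by default, interview only under the stated exception.
2. State in 10.3.9 that the completer is the participant.
3. Reconcile the home option in the COVID-19 Appendix with the manual text quoted in 8.1.2, for example by labelling it a documented departure from the manual.
4. Record the mode (self, interview, home) at each assessment. For assessments already done, recover it from site records and the COVID-19 flags where possible. Tabulate mode by arm and visit.
5. If an ANCOVA restricted to participants who self-completed at baseline and Week 24 is run, label it exploratory and give the reason.
6. Separately, add region (Japan, non-Japan) to the Week 24 SGRQ ANCOVA beside the baseline score.

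The cost is a few sentences, one eCRF field, one table and one model term with a single degree of freedom. Recovering past mode takes some site effort and may be incomplete, so the table should show how many assessments have unknown mode.
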